### **5 STUDY POPULATION**

#### **5.1 Inclusion Criteria**

A patient will be eligible for study participation only if all of the following criteria apply:

1. Male and female patients aged 5 to  $\leq$ 17 years with HoFH as defined by any of the following criteria recommended by the Consensus Panel on Familial Hypercholesterolaemia of the EAS (Cuchel, Bruckert et al. 2014):
  - a. Genetic confirmation of 2 mutant alleles at the LDLR, apo B, PCSK9, or LDLRAP1 gene locus OR
  - b. An untreated LDL-C  $>500$  mg/dL (13 mmol/L) or treated LDL-C  $\geq 300$  mg/dL (8 mmol/L) together with either
    - Cutaneous or tendon xanthoma before age 10 years or
    - Untreated LDL-C levels consistent with heterozygous FH in both parents
2. Baseline LDL-C on LLT ( $C_{max}$  of LDL-C immediately prior to LA, if applicable) of either:
  - a.  $>160$  mg/dL (4.1 mmol/L, no documented CVD) or
  - b.  $>130$  mg/dL (3.4 mmol/L, established CVD defined as aortic valve disease and/or coronary atherosclerosis)
3. Body weight  $\geq 15$  kg or BMI and height both  $>10^{th}$  percentile according to WHO Growth Charts for Boys and Girls 5 to 19 Years of Age (see Appendix 4 *WHO Growth Charts*).
4. Patient and/or his/her legal representative has/have been informed, has/have read and understood the patient information/informed consent form, and has/have given written informed assent/consent.
5. Patient and/or his/her legal representative must be able and willing to follow study procedures and instructions, particularly that:

- a. LLT (including LA when applicable) must be stable for at least 6 weeks prior to Baseline (Run-in Period) and remain stable through Week 24±3 days (end of Efficacy Phase).
- b. The patient must be compliant with both the low-fat diet supplying <20% of energy (calories) from fat or <30 g fat, whichever is the lesser amount starting at the beginning of the Run-in Period and the dietary supplement regimen starting at Week -2 of the Run-in Period, both continuing until completion of the study (and during the EAP/administration of commercial product, when applicable).

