## 5.2 Exclusion Criteria

A patient will not be eligible to participate in this study, if any of the following criteria apply:

1. Other forms of primary hyperlipoproteinaemia and secondary causes of hypercholesterolaemia (e.g., nephrotic syndrome, hypothyroidism).
2. Contraindications for the use of lomitapide according to section 4.3 of the Summary of Product Characteristics (SPC included in the Lojuxta® SPC in lieu of an IB; see Section 18.1 *Source Documents*), such as hypersensitivity to the active substance or to any of the excipients listed in Section 6.1 of the SPC, known significant or chronic inflammatory bowel disease or malabsorption.
3. Moderate (Child-Pugh B, see Appendix 1 *Child-Pugh Score*) or severe hepatic impairment (Child-Pugh C), active liver disease and/or abnormal liver function tests at Screening (AST or ALT >1.5 x ULN and/or total bilirubin >1.5 x ULN in the absence of Gilbert's syndrome or AP >1.5 x ULN [based on appropriate age and gender normal values]).
4. Serum CK >2 x ULN.
5. Chronic renal insufficiency with glomerular filtration rate (GFR) <70 mL/min/1.73 m^2 calculated using the Schwartz formula (see Appendix 2 *Schwartz Formula*).
6. Uncontrolled hypertension (defined as mean systolic and/or diastolic blood pressure ≥95% of normal for age and sex) despite medical therapy.
7. New York Heart Association (NYHA) Class III or IV congestive heart failure.
8. Precocious/delayed puberty or endocrine disorder affecting growth (e.g., hypothyroidism, premature adrenarche).
9. History of drug abuse within the last 3 years or habitual alcohol consumption (defined as >1 ounce [28 g] of liquor or 4-ounce glass [113 g] of wine, or the equivalent, ≥3 times per week).
10. Life expectancy predicted to be <5 years.
11. History of a non-skin malignancy (with the exception of cervical cancer *in situ*) within 3 years prior to enrolment.

12. Treatment with any Investigational Medicinal Product (IMP) within 6 months or 5 times the terminal half-life of the corresponding IMP, whichever is longer, before Screening (Visit 1).
13. Patient is a dependent of the sponsor, of the investigational team or his/her immediate family.
14. Pregnant or nursing women.

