## Vital Signs

Vital signs, including systolic and diastolic blood pressure, heart rate, body temperature, and respiratory rate, will be measured at Screening (Visit 1), at Baseline (Visit 4), and at every visit thereafter (see Section 1.2 *Flow Chart of Study and Follow-up*). Blood pressure and heart rate will be measured after 5 minutes of rest in a sitting position.

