## 9.2 Re-screening

If the patient is a screen failure, he/she can be re-screened on 2 separate occasions within 2 weeks of the previous (re-)screening. The patient can only be re-screened for the purpose of repeating LDL-C (inclusion criterion 2), serum CK (exclusion criterion 4) or blood pressure (exclusion criterion 6) measurement(s), as deemed appropriate by the investigator, since these parameters might change within a short timeframe. A new screening for eligibility based on all other inclusion and exclusion criteria is not possible, because they are not expected to change

within a short timeframe. The patient must be reconsented for the re-screening procedure(s); however, to reduce study burden and blood draws in this paediatric patient population, other screening procedures must not be repeated. The patient will be assigned a new patient number.

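### Exclusion 6 sets its blood pressure limit below normal and names no reference, so normal blood pressure can meet its definition of uncontrolled hypertension

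*Protocol*

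**What the plan says.** Protocol Section 5.2, criterion 6, excludes: "Uncontrolled hypertension (defined as mean systolic and/or diastolic blood pressure ≥95% of normal for age and sex) despite medical therapy". The exclusion list in the synopsis (Section 1.1) has the same wording.

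Three other places bear on how the criterion is used:

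- Inclusion criterion 3 (Section 5.1) sets its BMI and height limits as a "percentile according to WHO Growth Charts for Boys and Girls 5 to 19 Years of Age" and points to an appendix holding those charts.
- Section 8.1.2, Vital Signs, describes how blood pressure is taken: "Blood pressure and heart rate will be measured after 5 minutes of rest in a sitting position". It gives no reference values.
- Section 9.2 limits re-screening to three measurements: LDL-C, and "serum CK (exclusion criterion 4) or blood pressure (exclusion criterion 6) measurement(s), as deemed appropriate by the investigator". It refers back to criterion 6 and adds no limit of its own.

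Eligibility is confirmed at Screening (Section 9.1.1) and again at Baseline (Section 9.4.1).

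**The concern.** The limit is written as a fraction of a normal value. Any fraction below one puts it under normal, so the bracket describes pressures that are not raised and then calls them uncontrolled hypertension. Nothing else in the protocol repairs this. *Normal* is not defined as a median, a range or an upper limit, and no blood pressure table is cited. Neighbouring criteria are better anchored: 3 and 5 cite the Child-Pugh and Schwartz appendices, and 4 uses a multiple of the upper limit of normal.

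The study seeks about 45 children with a rare disease at approximately 15 sites in at least six countries. One site may apply the bracket as written while another guesses that a percentile was meant. The same child could then be a screen failure at one site and enrolled at the other, with both claiming to follow the protocol. A blood pressure failure can be re-screened on only two occasions, each needing new consent and a new patient number. Under Section 13.2 the monitor records patients enrolled without meeting every criterion as protocol deviations, so a literal reading could also generate deviations for children with ordinary pressures.

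**Working it through.** **1. The limit itself.** Limit = 0.95 × normal. A child at 1.00 × normal satisfies 1.00 ≥ 0.95 and meets the bracket. This needs no assumption about what *normal* means.

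**2. How many normotensive children reach the limit.** The protocol gives no blood pressure distribution, so every input here is an assumption:

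- blood pressure is normally distributed within age and sex, scaled so that the median is 1;
- the coefficient of variation (CV) is 6% to 15%, the same for systolic and diastolic;
- the systolic-diastolic correlation is 0.3 to 0.7;
- *normotensive* means below the 95th centile, which is 1 + 1.645 × CV;
- *normal* is either the median or that 95th centile, taken as an upper limit.

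*Normal read as the median, one measure.* The share of all children is P(Z ≥ −0.05/CV). The share of those below the 95th centile is (that share − 0.05)/0.95.

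- CV 6%: 0.798, then (0.798 − 0.05)/0.95 = 0.787.
- CV 15%: 0.631, then (0.631 − 0.05)/0.95 = 0.611 before further rounding.

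*Normal read as the upper limit, one measure.* The share of all children is P(Z ≥ (0.95 × (1 + 1.645 × CV) − 1)/CV).

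- CV 6%: 0.233, then (0.233 − 0.05)/0.95 = 0.193.
- CV 15%: 0.109, then (0.109 − 0.05)/0.95 = 0.062.

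*Systolic and/or diastolic.* This was simulated as a bivariate normal with 400,000 draws, among children below the 95th centile on both measures. The three values in each cell are for correlations 0.3, 0.5 and 0.7.

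| CV | Normal = median | Normal = upper limit |
|---|---|---|
| 6% | 0.926 / 0.903 / 0.875 | 0.317 / 0.294 / 0.270 |
| 8% | 0.884 / 0.856 / 0.824 | 0.223 / 0.206 / 0.188 |
| 10% | 0.852 / 0.822 / 0.785 | 0.173 / 0.161 / 0.145 |
| 12% | 0.828 / 0.796 / 0.758 | 0.140 / 0.131 / 0.119 |
| 15% | 0.801 / 0.766 / 0.728 | 0.112 / 0.103 / 0.093 |

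**3. Like for like.** On one measure, about 61% to 79% of normotensive children meet the bracket if normal is the median, and about 6% to 19% if it is an upper limit. On either measure, which is what the criterion specifies, the ranges are about 73% to 93% and about 9% to 32%.

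**4. What the shares do not include.** They apply to the bracket alone, before the words on medical therapy. The protocol does not say how many candidates take blood pressure treatment, so the share of candidates affected cannot be derived.

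**The case against.** A reader might infer that the criterion, taken literally, excludes most normotensive children. The documents do not support that, for two reasons. The sentence ends with a condition on medical therapy, so read as a whole it may reach only children under treatment, and an untreated child with ordinary pressure is not clearly excluded. Also, *most* holds only if normal is a central value. An upper limit is a plausible reading, since criteria 3 and 4 are written against upper limits of normal, and under it the share is well below half.

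It can also be said that the label and the reference to age and sex steer an investigator away from excluding ordinary readings, and that re-screening softens the effect of a single value. The consequences for the analysis are limited too. Section 12.2 defines the full analysis set by dosing and LDL-C measurements, not by eligibility. Meeting the eligibility criteria is a per-protocol condition, but exclusions are decided case by case at a data review meeting, and that set serves only sensitivity and supplementary analyses.

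All of this stands as a limit on the size of the problem. It does not remove the error: even for a treated child, a normal pressure would count as uncontrolled. That sites would probably guess a sensible meaning is no defence of an eligibility rule whose words say something else.

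**Conclusion.** The point holds as a wrongly stated threshold in an operative eligibility rule. It is certain from the text that the limit lies below normal, has no named reference and conflicts with its own label, in both places where it appears. The number of children it would catch is uncertain. The shares of about 61% to 93% (median) and about 9% to 32% (upper limit, either measure) rest on the assumed distribution and apply only where a site uses the bracket alone. Actual wrongful exclusion is a possibility, not a demonstrated effect. The risk is uneven enrolment and avoidable re-screening or deviations, not a biased primary test. The line should be corrected.

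**What to change.** Reword criterion 6 in Section 5.2 and in the synopsis so that:

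- the limit is consistent with the label of uncontrolled hypertension;
- it is tied to a named age- and sex-specific blood pressure reference, as inclusion criterion 3 does for BMI and height;
- it states whether a child not on blood pressure treatment is covered.

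A possible frame, with the blanks left to the sponsor: *mean systolic and/or diastolic pressure at or above [limit] in [named reference] for age and sex, in patients [on treatment / whether or not on treatment]*. The sponsor's clinicians must confirm the intended limit; none is proposed here. Section 9.2 refers to criterion 6 by number and needs no change.

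The cost is one line in two places, with no added procedures for patients and no change to the analysis. Because it alters an eligibility criterion, it goes through the amendment process in Section 15, with submission to the ethics committees and regulatory agencies and approval awaited where applicable. It could be combined with another amendment.

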## 6 STUDY MEDICATION

### 6.1 Description of the Investigational Product

#### 6.1.1 *Formulation, Packaging and Labelling*

The investigational product will be supplied in high-density polyethylene bottles with polyester, aluminium foil, and cardboard induction seals and child-resistant polypropylene screw caps. It will be packed and labelled according to applicable regulatory requirements.

Lomitapide is prepared as a crystalline methanesulfonate salt. The investigational product will be administered orally in opaque, hard gelatin capsules. Four bottle types will contain 28 capsules each by 2 mg, 5 mg, 10 mg, and 20 mg strength. Each hard capsule contains lomitapide mesylate equivalent to its strength and the following inactive excipients: pregelatinised starch (maize), sodium starch glycolate (Type A), microcrystalline cellulose, lactose monohydrate, colloidal, anhydrous silica, and magnesium stearate.

Please refer to the Lojuxta® SPC in lieu of an IB and to the Investigational Medicinal Product Dossier for the 2 mg lomitapide hard capsules regarding the excipients and colours of the capsule shells, which differ by strength (see Section 18.1 *Source Documents*). Further details regarding physical, chemical, and pharmaceutical properties and concerning the formulation, respectively are described in the EPAR Lojuxta® dated 30 May 2013, Section 2.2.

Please refer to Section 2.2 *Investigational Product* for further details regarding the mechanism of action and therapeutic indication of lomitapide.

#### 6.1.2 *Storage and Stability*

Keep the bottle tightly closed in order to protect from moisture. Store below 30°C.

#### 6.1.3 *Drug and Dietary Supplements Accountability*

A sufficient number of lomitapide bottles will be provided to sites in bulk at appropriate intervals depending on the phase of the study and accrual of patients. Dietary supplements will be sourced locally, where possible (see Section 6.3 *Dietary Supplements*). The investigator, or the person designated by the investigator, will be responsible for dispensing the appropriate bottle or combination of bottles to a patient at each study visit. At each site, the investigator, or the person designated by the investigator, will be responsible for keeping accurate records of study medication accountability comprising the receipt, the dispensing, and the return of all used and partially unused study medication throughout the study. The drug accountability form should be kept up to date and will be reviewed periodically by the study monitor. Patients will be asked to keep all used and partially unused bottles of study medication and return them to the site during the scheduled visits. For drug accountability, the number of used and partially unused bottles and unused capsules will be counted. Compliance with dietary supplements is discussed with the patients at each visit and is documented in the electronic Case Report Form (eCRF). It is also verified by reviewing the patient Diet Records (see Section 8.6.1 *Diet Instructions and Diet Records*). After drug accountability is completed, all unused or partially used study medication may be returned to the sponsor or disposed of by the study site. The study monitor will instruct the site on the return of all study medication. A final inventory of the total amount of study medication and dietary supplements at each study site against the

amount used and returned must be recorded. Inventory records must be readily available for inspection by the study monitor and/or auditor, and open to government inspection at any time.

## 6.2 Investigational Product Compliance

Patients and their parents/legal guardians will be instructed to return all unused study medication and dietary supplements to the clinical site at the visits indicated in Section 1.2 *Flow Chart of Study and Follow-up*. Site study team members will count and record the number of capsules remaining in each of the bottles and record this information on the eCRF. Study drug compliance checks will be performed at all visits during the Efficacy and Safety Phases of the study.

## 6.3 Dietary Supplements

Patients will be administered daily oral supplementation with vitamin E (200 IU for patients 5 to 8 years of age, 400 IU for patients 9 to ≤17 years of age) and an EFA supplement containing approximately 200 mg linoleic acid, 210 mg ALA, 110 mg EPA, and 80 mg DHA. Dietary supplements will be dispensed during Visit 3 at Week -3 to Week -2 (Run-in Compliance), during Visit 4 at D0 (Baseline, Efficacy Phase), and at every visit thereafter until Visit 21 at Week 92±1 week. Please refer to Section 6.1.3 *Drug and Dietary Supplements Accountability* for dietary supplements accountability.

# 7 STUDY TREATMENT

## 7.1 Treatment Assignment, Blinding Procedure

This is an open-label study, blinding of treatment is not applicable.

## 7.2 Treatment Schedule

After stabilisation of the patient on his/her current MTD of LLT (including LA when applicable) during the 6-week Run-in Period, treatment with lomitapide will be started as add-on therapy on D0 of the Efficacy Phase.

Lomitapide capsules will be provided in 4 dose strengths of 2 mg, 5 mg, 10 mg, and 20 mg. Dosing will be initiated at the recommended starting dose and escalated to the maximum dose as applicable to the age groups (see Table 2 and Figure 3) based upon safety and tolerability in addition to LDL-C values.

**Table 2 Lomitapide Starting Dose and Dose Escalation by Age Group**

Age Group (years)	Lomitapide Dose (mg)					Maximum
	D0	Week 4 ±3 days	Week 8 ±3 days	Week 12 ±3 days	Week 16 ±3 days	
5 to 10	2	2	5	10	20	20 (10, in Child-Pugh A)
11 to 15	2	5	10	20	40	40 (20, in Child-Pugh A)
16 to ≤17	5	10	20	40	60	60 (40, in Child-Pugh A)

Each patient will take 1 to 3 capsule(s) once daily to achieve the doses specified in the titration scheme. The first dose of study medication will be administered at the study site on D0.

As of D1, patients will self-administer (or the patient's parent/legal guardian will administer to the patient) lomitapide orally, once daily, at approximately the same time each day. It is recommended to administer lomitapide at least 2 hours after the evening meal (e.g., at bedtime) with a glass of water on an empty stomach because the fat content of a recent meal may adversely impact GI tolerability. Patients who are unable to swallow the intact capsule(s)

may open the capsule(s) and sprinkle the capsule content on 1 tablespoon of apple sauce or mashed banana, which are fat-free.

In case of a missed dose, patients should be instructed to take missed doses of lomitapide only if they can be taken at least 12 hours prior to the next scheduled dose. Dietary supplements are suggested to be taken in the morning. Patients taking bile acid sequestrants should be reminded that they should take lomitapide 4 hours before or 4 hours after this class of medications. If atorvastatin is given concomitantly, lomitapide should be administered 12 hours apart.

## 7.3 Dose Modifications and Interruptions

### 7.3.1 Dose Escalation, Dose Reduction and Re-challenge

#### Dose Escalation

Patients will be categorised according to disease severity as determined by the presence or absence of clinically evident CVD, which will be defined by documented aortic valve disease or coronary atherosclerosis at Baseline.

Lomitapide will not be escalated, if LDL-C is less than the target threshold:

- LDL-C is <100 mg/dL (<2.5 mmol/L) in patients without CVD at Baseline
- LDL-C is <70 mg/dL (<1.8 mmol/L) in patients with CVD at Baseline

For each of the 3 age groups, lomitapide dosing will escalate following the applicable dose titration scheme in Table 2 at Week 4±3 days, Week 8±3 days, and Week 12±3 days to the maximum allowable dose by Week 16±3 days or the MTD by Week 20±3 days based upon acceptable safety and tolerability criteria in addition to LDL-C values.

Each dose must be tolerated for ≥4 consecutive weeks before being escalated to the next higher dose in stepwise increments. The MTD is defined as the highest dose of lomitapide through Week 24±3 days that does not result in tolerability or safety concerns. This is the highest dose that does not result in dose reduction, dosing interruption, or discontinuation, but may include a re-challenged dose level.

Each patient will continue receiving the MTD of lomitapide he/she achieved during the Efficacy Phase (unless criteria is met for reducing or increasing the dose) for an additional 80±1 weeks in the Safety Phase (for a total treatment period of 2 years).

If after Week 24±3 days both the investigator and the sponsor consider a patient 5 to 15 years of age to be eligible for further escalation of the lomitapide dose beyond the maximum recommended dose by the respective age group, the lomitapide dose can be increased to an extent defined by the investigator after consultation with the sponsor based on individual safety, efficacy, and concomitant LLT criteria. If the patient tolerates this new dose for ≥4 weeks, then this will be considered the new MTD.

If after Week 24±3 days, a patient has crossed over into the next age category, the study medication can be escalated to the maximum dose applicable for the new age category. If the patient tolerates this new dose for a minimum of 4 weeks, then this will be considered the new MTD.

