## LIST OF TERMS AND ABBREVIATIONS

Term or Abbreviation	Description
AA	Arachidonic acid
ACTH	Adrenocorticotropic hormone
ADR	Adverse drug reaction
AE	Adverse event
AESI	Adverse Event of Special Interest
ALA	Alpha-linolenic acid
ALT	Alanine transaminase
ANCOVA	Analysis of covariance
AP	Alkaline phosphatase
apo A-I	Apolipoprotein A-I
apo B	Apolipoprotein B
ASCVD	Atherosclerotic cardiovascular disease
AST	Aspartate transaminase
ATC	Anatomical Therapeutic Chemical
BG	Blood glucose
BMI	Body mass index
BSA	Body surface area
BUN	Blood urea nitrogen
Ca	Calcium
CAS	Completer analysis set
CBC	Complete blood count
c-het	compound heterozygous
CIMT	Carotid intima-media thickness
CK	Creatinine kinase
Cl	Chloride
C max	Maximum concentration
C-R	Concentration-Response
CRP	C-reactive protein
CTCAE	Common Terminology Criteria for Adverse Events
CVD	Cardiovascular disease
CYP	Cytochrome P 450
D	Day(s)
DHA	Docosahexaenoic acid
DSMB	Data Safety Monitoring Board
EAP	Expanded Access Programme
EAS	European Atherosclerosis Society
EASL	European Association for the Study of the Liver
EC	European Commission
ECG	Electrocardiogram
eCRF	Electronic Case Report Form
EEA	European Economic Area
EFA	Essential fatty acids

Term or Abbreviation	Description
EMA	European Medicines Agency
EoT	End of Treatment
EPA	Eicosapentaenoic acid
EPAR	European Public Assessment Report
FAS	Full analysis set
FDA	Food and Drug Administration
FH	Familial Hypercholesterolaemia
FMD	Flow-mediated dilatation
FSH	Follicle stimulating hormone
GCP	Good Clinical Practice
GFR	Glomerular filtration rate
GGT	Gamma-glutamyl transferase
GI	Gastrointestinal
HDL-C	High-density lipoprotein cholesterol
HMG-CoA	3-hydroxy-3-methylglutaryl coenzyme A
HoFH	Homozygous familial hypercholesterolaemia
ICF	Informed Consent Form
ICH	International Council for Harmonisation of Technical Requirements for Pharmaceuticals for Human Use
IDL	Intermediate density lipoprotein
IEC	Independent Ethics Committee
INR	International normalised ratio
IRB	Institutional Review Board
ITT	Intent-to-treat (analysis set)
IU	International units
IV	Intravenous
K	Potassium
LA	Lipoprotein apheresis
LDL	Low-density lipoprotein
LDL-C	Low-density lipoprotein cholesterol (conventional mg/dL units can be converted to SI [mmol/L] units using the factor 0.0259)
LDLR	LDL receptor
LDLRAP1	LDL-receptor adapter protein 1
LFT	Liver function test
LH	Luteinising hormone
LLT	Lipid-lowering therapy (including LA, where applicable)

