### Dose escalation by age group

Age Group (years)	Lomitapide Dose (mg)					
	D0	Week 4	Week 8	Week 12	Week 16	Maximum
5 to 10	2	2	5	10	20	20 (10, in Child-Pugh A)
11 to 15	2	5	10	20	40	40 (20, in Child-Pugh A)
16 to ≤17	5	10	20	40	60	60 (40, in Child-Pugh A)

- Lomitapide will not be escalated, if LDL-C is less than the target threshold:
  - LDL-C is <100 mg/dL (<2.5 mmol/L, in patients without CVD at Baseline)
  - LDL-C is <70 mg/dL (<1.8 mmol/L, in patients with CVD at Baseline)
- Dose must be tolerated for ≥4 consecutive weeks before escalation to the next higher dose.
- If a dose reduction is required, dosage will either be reduced to the previous tolerated dose or to an intermediate dose. Please note that only down-tiltrations to intermediate doses are allowed, dose escalations need to follow the guidance provided in the table above. After resolution of the cause for dose reduction, patients may be re-challenged after a minimum period of 4 weeks following dose reduction with prior doses in stepwise increments based on dose escalation guidelines, but may not exceed the MTD established during the Efficacy Phase until Week 24±3 days, after which further increase is only possible if patients have crossed into the next age category or if both the investigator and the sponsor consider a patient 5 to 15 years of age to be eligible for further escalation of the lomitapide dose beyond the maximum recommended dose by the respective age group based on individual safety, efficacy, and concomitant LLT criteria.

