## 2.6.2 Known and Potential Benefits

Lomitapide is a first in class oral, selective MTP inhibitor that functions independently of the *LDLR*. It is administered orally and is subject to a high first-pass effect following ingestion resulting in a low systemic bioavailability of approximately 7% (see Section 2.3.3 of the EPAR for Lojuxta® dated 30 May 2013). The pharmacodynamic activity of lomitapide is not dependent on systemic exposure but is directly related to local concentrations achieved in the small intestine and liver.

The high first-pass effect observed to limit systemic availability of lomitapide is likely to be dominated by significant metabolism by CYP 3A4 inhibitors. The parent molecule is cleaved into 2 primary metabolites (M1 and M3) that lack activity against MTP. Systemic concentrations of lomitapide are low following oral administration and there is a large apparent volume of distribution despite a high level of protein binding. This suggests loose binding to low-affinity sites, mitigating the likelihood of interactions by displacement of other protein-bound drugs. Excretion of unchanged lomitapide is minimal by any route, and the majority of the drug appears as water soluble (polar) metabolites in the bile.

Therefore, strong or moderate CYP 3A4 inhibitors are not permitted during the study as described in Section 7.6.3 *Non-Permitted Concomitant Medication, Food or Substances*. Weak CYP 3A4 inhibitors are only permitted during the Safety Phase of the study and doses of lomitapide or concomitant medication should either be administered 12 hours apart or modified (see Section 7.3.3 *Dose Modification for Concomitant Medication*).

The central role of LDL-C in the pathophysiology of ASCVD is well established. Every 1 mmol/L (38.6 mg/dL) reduction in LDL-C levels is associated with a corresponding 22% decrease in cardiovascular mortality and 12% reduction in total mortality over 5 years (Baigent, Blackwell et al. 2010).

Published evidence shows lomitapide to reduce LDL-C consistently and significantly by a mean 40% to 50% across the whole spectrum of molecularly-defined adult HoFH patients irrespective of LA and independent of *LDLR* function. There was no loss of efficacy in patients with genotypes predicting the most severely compromised *LDLR* function, who tend to be non-responsive to other therapies like statins and PCSK9 inhibitors (Hegele, Shah et al. 2018).

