#### Dose Reduction and Re-challenge

If a dose reduction is required, dosage will either be reduced to the previous tolerated dose or to an intermediate dose. Please note that only down-titrations to intermediate doses are allowed, dose escalations need to follow the guidance provided in Table 2. After resolution of the cause for dose reduction, patients may be re-challenged after a minimum period of 4 weeks following dose reduction with prior doses in stepwise increments based on dose escalation guidelines, but may not exceed the MTD established during the Efficacy Phase until

Week 24±3 days, after which further increase is only possible if patients have crossed into the next age category or eligibility for exceptional dose escalation as described above is met.

If the investigator determines that a patient is not tolerating any particular dose (per specified criterion), the investigator may request a dose reduction or a hold on the current dose until the next scheduled visit. Once the patient has stabilised on the reduced dose, the dose can be increased back to the next step again, and the patient may progress through subsequent dose increases at a minimum of 4-week intervals. If the patient does not tolerate the re-challenge dose, then the MTD is considered the reduced dose and will be the highest dose allowed for the remainder of the study.

Weeks 0 through 24±3 days establish the MTD, Week 20±3 days is the last visit that the lomitapide dose can be increased, except when there has been a down-titration at/or after Week 16±3 days. Re-challenging will depend on the assessment of safety and tolerability criteria and the LDL-C value relative to the LDL-C goal of <135 mg/dL (3.5 mmol/L) and is at the discretion of the investigator except for Hy's law cases or comparable signs of liver toxicity, irrespective of origin, in which no re-challenge will be allowed (see Section 7.4 *Patient Discontinuation Criteria*).

The study medication can be escalated as a re-challenge dose during an unscheduled visit after the investigator consults with the study medical monitor, but any additional dose escalations, i.e., dose titration, must be made during a completed scheduled visit. In addition, a re-challenge with lomitapide will not be performed if the LDL-C is below the target threshold while the patient was receiving the reduced dose.

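### The no-escalation limit for patients without CVD pairs 100 mg/dL with 2.5 mmol/L, but by the protocol's own factor 100 mg/dL is 2.59 mmol/L, so the two printed limits conflict between 96.5 and 100 mg/dL

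*Protocol*

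**What the plan says.** Section 7.3.1 (Dose Escalation) sets an LDL-C level below which lomitapide is not escalated. For patients without cardiovascular disease at Baseline the limit reads "LDL-C is <100 mg/dL (<2.5 mmol/L) in patients without CVD at Baseline". The synopsis (Section 1.1, Dose escalation by age group) gives the same pair: "LDL-C is <100 mg/dL (<2.5 mmol/L, in patients without CVD at Baseline". For patients with CVD both places print 70 mg/dL with 1.8 mmol/L. Above the limit, escalation follows the titration table "based upon acceptable safety and tolerability criteria in addition to LDL-C values".

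The same threshold reappears under Dose Reduction and Re-challenge: "a re-challenge with lomitapide will not be performed if the LDL-C is below the target threshold while the patient was receiving the reduced dose". Re-challenge also depends on "the LDL-C value relative to the LDL-C goal of <135 mg/dL (3.5 mmol/L) and is at the discretion of the investigator".

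The protocol states the unit conversion twice. The entry for LDL-C in the List of Terms and Abbreviations says that "conventional mg/dL units can be converted to SI [mmol/L] units using the factor 0.0259", and Section 2.6.2 contains "Every 1 mmol/L (38.6 mg/dL) reduction in LDL-C levels". Section 10 has the lipid panel run in local hospital laboratories as well as centrally, and says that the local results serve treatment decisions. It does not state the units in which those laboratories report.

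**The concern.** In the escalation rule both figures carry their own inequality sign, so each can be read as a limit in its own right. If they are not the same concentration, a patient whose LDL-C falls between them is barred from escalation under one unit and allowed it under the other. A site whose laboratory reports mmol/L would naturally apply the mmol/L figure.

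What is at stake is a dose step in a child. In Table 2 ("Lomitapide Starting Dose and Dose Escalation by Age Group") nearly every step raises the dose by at least half. A secondary consequence is that for an escalation made inside the gap the text cannot settle whether the protocol was followed, although the monitor must record incorrect doses as deviations (Section 13.2).

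**Working it through.** **Inputs, all from the Protocol.** Printed limit for patients without CVD: 100 mg/dL and 2.5 mmol/L (Sections 7.3.1 and 1.1). Conversion: mmol/L = mg/dL × 0.0259 (List of Terms and Abbreviations), or 38.6 mg/dL per mmol/L (Section 2.6.2).

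**Trying to reproduce the printed figure.**

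- Forward: 100 × 0.0259 = 2.59 mmol/L, which is 2.6 to one decimal. The printed 2.5 is not reproduced.
- Backward: 2.5 / 0.0259 = 96.5 mg/dL.
- With the second statement of the conversion: 100 / 38.6 = 2.59 mmol/L and 2.5 × 38.6 = 96.5 mg/dL. The two sources agree.
- Gap: 100 − 96.5 = 3.5 mg/dL, or 3.5% of the limit.

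**Could it be rounding?** A figure printed as 2.5 covers 2.45 to 2.55 mmol/L, which is 94.6 to 98.5 mg/dL. That range excludes 100. The protocol's other LDL-C limits serve as controls:

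| mg/dL | × 0.0259 | Printed mmol/L | Rounds to the printed figure? |
|---|---|---|---|
| 70 | 1.813 | 1.8 | yes |
| 100 | 2.590 | 2.5 | **no** |
| 130 | 3.367 | 3.4 | yes |
| 135 | 3.497 | 3.5 | yes |
| 160 | 4.144 | 4.1 | yes |
| 300 | 7.77 | 8 | yes |
| 500 | 12.95 | 13 | yes |

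The partner limit in the same rule converts back to 1.8 / 0.0259 = 69.5 mg/dL, a gap of 0.5 mg/dL from ordinary rounding.

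**Where the two limits give opposite answers.** At 98 mg/dL, 98 × 0.0259 = 2.54 mmol/L. This is below 100 mg/dL, so escalation is forbidden, but not below 2.5 mmol/L, so it is allowed. For a laboratory that reports mmol/L:

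- One decimal: 2.4 (92.7 mg/dL) is forbidden by both limits, 2.5 (96.5 mg/dL) is in conflict, and 2.6 (100.4 mg/dL) is allowed by both.
- Two decimals: the nine values from 2.50 (96.5 mg/dL) to 2.58 (99.6 mg/dL) are in conflict; 2.59 (100.0 mg/dL) is not.

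**What a step means.** Ratios of successive doses in Table 2 are 1, 2.5, 2, 2 for ages 5 to 10; 2.5, 2, 2, 2 for ages 11 to 15; and 2, 2, 2, 1.5 for ages 16 to 17. Of the 12 scheduled steps, 11 change the dose, by a factor of 1.5 to 2.5. The exception is the Week 4 step in the youngest group, which stays at 2 mg.

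**Is the band reachable?** As an illustration only: patients without CVD enter above 160 mg/dL (Section 5.1). A 40% fall, the adult intent-to-treat mean in Section 2.4.2, takes an entry value of 161 mg/dL to 161 × 0.6 = 96.6 and one of 166 mg/dL to 166 × 0.6 = 99.6, both inside the band.

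**The case against.** The strongest reply is that this is a familiar guideline pair rather than a failed calculation. Section 2.1.1 gives 100 mg/dL with 2.5 mmol/L as the European Atherosclerosis Society's target for adults, and the pair recurs in the background sections. That probably explains where it came from. As a background target it decides nothing; in a dosing rule it has to give one answer, and it gives two.

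It can also be said that mg/dL is printed first throughout and that the abbreviation list converts from mg/dL to mmol/L, so mg/dL is the source unit. That is a reasonable inference, but the protocol never states it, and a site working in mmol/L need not draw it.

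Correctly rounded pairs leave gaps too. The diagnostic limit of 300 mg/dL with 8 mmol/L converts back to 308.9 mg/dL, a gap of 8.9 mg/dL. This is true, and the size of the gap at 100/2.5 is not unique. What sets that pair apart is that the printed mmol/L figure is wrong at its own precision.

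Finally, the practical exposure is small. It needs a patient without CVD, an LDL-C inside a 3.5 mg/dL band at a titration visit, a step still available, and a site reading mmol/L. The step would be the next scheduled one, after at least four weeks' tolerance of the current dose and within the age maximum. The mmol/L reading permits escalation but does not require it. All of this stands, and it limits the weight of the point without removing the conflict.

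**Conclusion.** The point holds, as a minor one. The mmol/L figure in the no-escalation rule for patients without CVD is wrong by the protocol's own factor, and from 96.5 to just under 100 mg/dL the rule gives opposite answers in the two units. The arithmetic needs no outside assumption.

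How often this would matter cannot be derived from the protocol, because the sites' reporting units are not stated and patients with CVD use the other limit. The number of affected decisions is small and may be zero. Re-challenge is touched only secondarily: a child in the band is already below the 135 mg/dL goal, and the investigator has discretion there. The target-attainment endpoint uses 135/3.5, which converts correctly. Power, sample size and the primary analysis are unaffected.

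**What to change.** In Section 7.3.1 and in the synopsis, replace 2.5 mmol/L by 2.59 mmol/L in the limit for patients without CVD. If one decimal is preferred, print 2.6 mmol/L; since 2.6 / 0.0259 = 100.4 mg/dL, this leaves a gap of 0.4 mg/dL, comparable with the 70/1.8 limit. Add one sentence stating that the mg/dL limits govern and that results reported in mmol/L are converted with 0.0259 before the rule is applied.

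Nothing in the protocol suggests that 96.5 mg/dL was the intended limit, so the mmol/L figure is the one to correct. The cost is one figure in two places and one sentence, with no change to procedures, data collection or analysis.
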